## 6.1 Human Subjects' Protections and Risks

Risks of study participation and medications are described in detail in the informed consent, as are protections and the participant's right to not participate or withdraw at any time.

## 6.1.2 Pulmonary Function Tests

PFTs are a common medical procedure of generally low risk. Some participants may experience breathlessness, cough, fatigue, dizziness/lightheadedness (hyperventilation), all of which are brief and very rarely headache, syncope, musculoskeletal chest pain, rib fractures, or ear injury. An episode of stress incontinence (urine leakage) may be caused by the PFT maneuvers in susceptible individuals. A seated position has been specified to reduce risk related to dizziness or syncope. Transmission of airborne disease is rare and minimized or eliminated with single-use filters. Instructions for withholding bronchodilator medications prior to testing stress the continued use of rescue medication if needed. The use of albuterol or ipratropium generally relieves any symptoms related to the trough effect of long-acting bronchodilators.

• Albuterol has been reported to cause urticaria, angioedema, paradoxical bronchospasm, angina, arrhythmias, QT prolongation, hypertension, hypokalemia, seizures, tremor, nervousness, headache, tachycardia, muscle cramps, palpitations, insomnia, and dizziness.

- Ipratropium has been reported to cause cough, nausea, dry mouth, dizziness, headache, dyspnea, atrial fibrillation, tachycardia, paradoxical bronchospasm, laryngospasm, angioedema, anaphylaxis, hypersensitivity, and exacerbate narrow-angle closure glaucoma.
- The dose used in testing is twice the usual dose of albuterol (one dose every four hours) or ipratropium (one dose every six hours) used chronically. However, home management of exacerbations includes increasing the dose and/or frequency of bronchodilator therapy. Doses in patients hospitalized or visiting the Emergency Department for exacerbations may be ten times the usual dose. Repeat dosing after at least three hours, is unlikely to result in any additional side effects, if necessary for the scheduling of the computed tomography.

The six-minute walk test is self-paced, but participants are encouraged to cover as much distance as they can in six-minutes. As with any walk, the participant may stumble or fall. It is expected that more severe participants will become short of breath and may need to stop to recover before six minutes have elapsed. The walk test will be stopped if the participant's SaO2 falls below 80%.

## 6.1.3 Imatinib side effects

The most common side effects of imatinib include nausea, diarrhea, headaches, leg cramps, fluid retention, visual disturbances, rash, weight gain, and reduced number of blood cells (any cell line can be affected). Imatinib is an immune suppressant and increases risks of common and uncommon infections.

Severe systolic congestive heart failure is an uncommon but recognized side effect of imatinib and mice treated with large doses of imatinib show toxic damage to myocardiocytes. Hypoxemia has been noted in one individual with LAM.

Since imatinib is mainly metabolised via the liver enzyme CYP3A4, substances such as ketoconazole, itraconazole, clarithromycin, and grapefruit juice can increase the plasma concentration of the drug. Conversely, CYP3A4 inducers like rifampin and St. John's Wort reduce the drug's activity. These medications will be prohibited during the study. A known interaction between imatinib and sirolimus in which sirolimus levels rise will be monitored during the study.

Imatinib also acts as an inhibitor of CYP3A4, 2C9 and 2D6, increasing the plasma concentrations of simvastatin, cyclosporin, pimozide, warfarin, and metoprolol. Imatinib also reduces plasma levels of levothyroxin via an unknown mechanism. INR, Cholesterol, T4, and TSH will be measured during the study for all individuals.

An imatinib dose reduction to 200 mg daily will be permitted should a participant experience persistent side effects.

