## 2.2 Rationale for the Study

The proposed study design is a prospective, multicenter, randomized, stratified, double blind, placebocontrolled, proof of principal trial to examine the effect of imatinib mesylate on intrasubject VEGF-D, a biomarker associated with LAM disease activity. Since imatinib mesylate has not previously been used in LAM, a small pilot study is needed to gather safety data, confirm biomarker efficacy data, and determine if a clinical efficacy signal can be obtained in a short term study.

This pilot trial employs a dual agent design intended to generate safety and efficacy data sufficient to power and design a phase 3 study of imatinib mesylate vs placebo for LAM. Durability of response will not be tested. Importantly, VEGF-D level will be used in this small clinical trial design using 20 participants.

Since LAM is a rare disease a small trial is designed to assure enrollment is achievable.

This study will enable proper powering of subsequent studies. The authors believe that a proof of principal pilot study will be able to recruit 20 participants, the majority on rapamycin, for this study.

The overarching hypothesis that imatinib mesylate kills LAM cells, while sirolimus (rapamycin) provides growth suppression, suggests that removal of rapamycin may be necessary for the effects of imatinib mesylate to be seen. Therefore, a two stage pilot study has been designed with usual doses of imatinib mesylate used for other indolent tumors, in an attempt to confirm the hypothesis.

The findings of this pilot study are expected to enable powering of a larger clinical trial and advance knowledge of pathogenesis and treatment of LAM. All results will be shared at the end of the study with the LAM community.

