## 5.5.2 Pulmonary Function Testing and Exercise Tests

These are performed at each study visit.

Comprehensive lung function testing is obtained at each visit in this study. Baseline spirometry is obtained by following ATS guidelines. Post bronchodilator spirometry is obtained with an aggressive protocol of 4 puffs of albuterol and 4 puffs of ipratroprium to allow an optimal assessment. Lung volumes are obtained by plethysmography and diffusion capacity by the single breath method.

A 6MWT is performed at each of the 3 study visits. The 6MWT is performed without supplemental oxygen by methodology of the ATS Standards. Desaturation less than 80% has been associated with some adverse events and will be used to stop the test and measure the distance should that event occur. Oxygen saturation is determined throughout the entire test. A 10 point Borg dyspnea scale is obtained at rest and at the end of the 6MWT.

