## 7.3.3 Exploratory endpoints

The table below lists the exploratory endpoints that will be collected to define if there is a difference between the 4 populations in the study. All change variables are measured intrasubject.

Efficacy Endpoints	Difference in baseline and 1 month after initiation of monotherapy imatinib/placebo	Difference in baseline and 1 month in patients on sirolimus	Difference in baseline and 2 months in imatinb naive participants
Change in VEGF-D (log pg/ml)	X (Primary)	X (Exploratory)	X (Secondary)
Change in FVC (%)	X (Secondary)	X (Exploratory)	X (Exploratory)
Change in FEV1 (%)	X (Secondary)	X (Exploratory)	X (Exploratory)
Change in mMRC Dyspnea (score)	X (Exploratory)	X (Exploratory)	X (Exploratory)
Change in 6MWT distance (M)	X (Exploratory)	X (Exploratory)	X (Exploratory)
EQ-5D (score)	X (Exploratory)	X (Exploratory)	X (Exploratory)
Functional Assessment	X (Exploratory)	X (Exploratory)	X (Exploratory)

Inventory (score)			
SGRQ (score)	X (Secondary)	X (Exploratory)	X (Exploratory)

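### Hypoxemia is listed under imatinib side effects with a LAM case, yet walk oxygen saturation and DLCO are never summarised by randomised arm

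*Combined protocol and SAP*

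**What the plan says.** Section 6.1.3 (Imatinib side effects) gives a list of general effects of the drug and one sentence tied to a person with this disease: "Hypoxemia has been noted in one individual with LAM". Section 2.2 justifies the pilot with the words "Since imatinib mesylate has not previously been used in LAM".

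On measurement, section 5.5.2 says "A 6MWT is performed at each of the 3 study visits", and that "The 6MWT is performed without supplemental oxygen by methodology of the ATS Standards". It adds "Oxygen saturation is determined throughout the entire test". The same section has lung volumes and single-breath diffusion capacity obtained at each visit.

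On use, section 5.5.2 says desaturation below 80% "will be used to stop the test and measure the distance should that event occur". Section 6.1.2 repeats the stopping rule. No other use of saturation is given.

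On analysis, section 7.3 and its endpoint table cover VEGF-D, FVC, FEV1, mMRC dyspnea, 6MWT distance, EQ-5D, the Functional Assessment Inventory and SGRQ. There is no row for saturation, stopped walks or DLCO. Section 6.3.1 declines a statistical plan for safety endpoints because numbers and observation time are too small, and says that adverse events will be reported with timing, severity and attribution. Safety of imatinib in LAM is nevertheless the third aim in section 3.2.

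**The concern.** The protocol names a possible oxygenation effect, measures oxygenation at every visit in a randomised placebo-controlled trial, and then plans no look at it by arm.

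Two things follow. First, the direct route to a finding is an adverse event report. Section 6.3 counts a laboratory value or change if it is clinically significant, and the plan sets no saturation level at which a reading becomes an adverse event. A drop during the walk that stays above 80% stops nothing and need not be filed. Second, a walk that is stopped has its distance taken at that point and enters the exploratory comparison of 6MWT distance with no flag. A gas-exchange effect would then read as lower exercise capacity.

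What is at stake is the safety description that this pilot is meant to hand to a later trial. No primary or secondary efficacy result is affected.

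**Working it through.** The documents give no saturation SD, hypoxemia rate or power figure, so there is nothing of the plan's own to reproduce. The check has two parts.

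**1. Where oxygenation goes in the plan**

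| Item | Measured | Stated use | By-arm summary |
|---|---|---|---|
| Walk saturation | 5.5.2, 3 visits, no supplemental oxygen | Stop below 80% (5.5.2, 6.1.2) | None in 7.3 or 6.3.1 |
| Walks stopped for desaturation | Implied by the stop | Distance is measured at that point | None |
| DLCO | 5.5.2, each visit | Entry criterion (5.3.1) | None |
| 6MWT distance | 5.5.2, 3 visits | Exploratory endpoint (7.3.3) | Yes, without a stopped-walk flag |

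Size of the distance effect, as an illustration: at constant speed a walk stopped at minute 4 scores 4/6 of the full distance, a loss of 1 − 4/6 = 33%.

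**2. What 10 per arm can show**

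Inputs: 10 imatinib and 10 placebo sets (section 6); two-sided 0.05 and a rank-sum test (section 7.2). The event rates and saturation SDs below are assumptions.

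*Events.*
- Fisher exact test, 0/10 against 4/10: p = 2 × C(10,4)/C(20,4) = 2 × 210/4845 = 0.087.
- 0/10 against 5/10: p = 2 × 252/15504 = 0.033. A two-sided p below 0.05 thus needs five events against none.
- Upper two-sided 95% limit for 0/10: 1 − 0.025^(1/10) = 30.8%.
- Chance of at least one event among 10 on imatinib, 1 − (1 − p)^10: 40%, 65% and 89% for assumed true rates of 5%, 10% and 20%.
- Fisher power is about 6% for assumed rates of 10% against 30%, and about 30% for 10% against 50%.

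*Continuous change.*
- Simulated power of the exact rank-sum test, 10 against 10, normal data: about 17% at 0.5 SD, 36% at 0.8 SD, 52% at 1.0 SD and 81% at 1.4 SD.
- For an assumed SD of change of 2 to 5 saturation points, 1.4 SD is 1.4 × 2 = 2.8 to 1.4 × 5 = 7.0 points.
- Half-width of the 95% interval for the difference in mean change: t(0.975, 18) × SD × √(2/10) = 0.94 × SD, or about 1.9 points at SD 2 and 4.7 points at SD 5.

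The continuous readings therefore yield an estimate with a stated width, where counts of 0 or 1 say almost nothing. Neither gives a reliable test of a moderate effect.

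**The case against.** The strongest reply is that the protocol says openly why it has no safety statistics: the numbers and follow-up are too small. It also has other ways to see respiratory harm. Participants are asked about adverse events at visits and in three telephone calls (6, 5.5.3), the DSMB reviews all adverse events quarterly (9.3), and mMRC and SGRQ are compared between arms (7.3.3). Lung volumes, Borg score and thyroid tests are likewise measured without an endpoint row. This stands in part: an oxygenation effect could surface by these routes. All are indirect, however, and none defines a saturation change. Saturation differs from the other unlisted measures because section 6.1.3 itself raises hypoxemia in LAM. Small size is also no reason against a descriptive table.

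A reader might infer three stronger things that the documents do not support.

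- *That hypoxemia is an established imatinib effect in LAM, so that 2.2 is false.* The sentence in 6.1.3 names no drug, dose or timing. Exposure to imatinib is implied only by the section title. The mismatch with 2.2 calls for clarification.
- *That the data could confirm or dispel the signal.* The power figures rule that out.
- *That everything needed is already recorded.* Section 5.5.2 has saturation determined during the walk, but does not name resting or lowest values as data items. The visit descriptions in 5.4 mention only post-bronchodilator spirometry, whereas 5.5.2 has diffusion capacity at each visit.

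The remedy has a limit of its own: because the walk stops below 80%, the lowest saturation a full walk would have reached is not observed in the most affected participants.

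**Conclusion.** The point holds as a reporting gap in the safety plan. The plan as written makes no comparison between arms of any measure of oxygenation, although it reports hypoxemia in a person with LAM under this drug's side effects, follows saturation at three visits, and has safety in LAM as an aim. A fall that stays above 80% and goes unfiled would be missed, and a stopped walk would be seen only as lost distance, 33% for a stop at minute 4 under constant speed.

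The size of any effect cannot be judged from the documents. With 10 per arm, zero events is compatible with a rate up to 30.8%. A difference in mean saturation change would be estimated to within about 1.9 to 4.7 points if the SD is 2 to 5 points and all 20 participants contribute; early withdrawals would widen this. A null finding would not rule out an effect. No planned efficacy test or sample size changes.

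**What to change.** 1. In the safety report, tabulate by randomised arm at the 1 month and 2 month visits: change from baseline in resting SpO2, change in lowest walk SpO2, number of walks stopped for desaturation, and change in DLCO. Give 95% confidence intervals and plots of individual participants. Put this in the safety report, because the columns of the 7.3.3 table use other comparisons and populations.
2. State that these summaries are descriptive, unadjusted for multiplicity and not a powered test.
3. Add resting SpO2, lowest walk SpO2 and a field for walks stopped for desaturation to REDCap.
4. Treat the lowest SpO2 of a stopped walk as censored below 80%. Give it the lowest rank, and summarise by medians or ranks where any walk was stopped.
5. Report 6MWT distance with the stopped-walk flag.
6. Make 5.4 and 5.5.2 agree on whether DLCO is obtained at follow-up visits.
7. Clarify whether the individual in 6.1.3 had received imatinib, reconcile that with 2.2, and tell the DSMB the answer.

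The cost is a few data fields, a handful of descriptive tables and one clarified sentence. No procedure, visit or stopping rule changes. The downside is that several small-sample summaries may be over-read, which the wording in item 2 should guard against.

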#### 6.1.4 Sirolimus side effects

The most common side effects of sirolimus are immune suppression, thrombocytopenia and impaired wound healing. For these reasons, individuals planning surgery (including oral surgery) during the study interval are excluded.

Lung toxicity is a serious complication associated with sirolimus therapy although it usually occurs shortly after beginning therapy. The mechanism of the interstitial pneumonitis is not clear. The toxicity does not appear to be dose dependent, but is more common in patients with underlying lung disease.

Sirolimus also acts on a related complex known as mTORC2. Disruption of mTORC2 produces the diabetes-like symptoms of decreased glucose tolerance and insensitivity to insulin also associated with sirolimus. As with all immunosuppressive medications, in theory sirolimus and imatinib may decrease the body's inherent anticancer activity. However, both of these medications have data that sirolimus can enhance the immune response to tumor targeting and promote tumor regression in clinical trials.

## 6.1.5 Vaccinations

Because both of these agents are immunosuppressants, live vaccinations are contraindicated because the microorganisms in the vaccine could multiply and infect the patient. Vaccines that are inactivated and toxoid vaccines do not hold this risk, but may not be effective during imatinib or sirolimus therapy.

## 6.2 Confidentiality

There is a risk to confidentiality. Source data at each center will be kept electronically under password protected systems. Questionnaires or paper documents will be kept in secure areas. Data transmission will be encrypted with a 128-bit VPN approach. The PFT software is designed to be HIPAA compliant for clinical use. Collection of DNA and RNA can lead to identification of patients.

All study personnel are certified in the ethical conduct of human biomedical and genetics research and HIPAA information security.

Longer descriptions of human subjects protections are provided in the consent form template.

## 6.3 Adverse Events

An adverse event (AE) is any untoward medical occurrence in a study subject. This may include symptom(s), illness, clinically significant abnormal laboratory value or change in value, or worsening in a subject during a clinical study. Since one of the specific aims of the study is to establish the safety of imatinib in LAM affected individuals, it is the goal of the investigators to capture every AE.

## 6.3.1 Procedures for Adverse Events

Event, date of onset, severity, duration, and relationship to sirolimus or imatinb (if it can be determined) will be recorded on the study AE forms. All adverse events will be followed until they are adequately resolved or stabilized, or for 1 month following study completion, whichever comes first.

If an adverse event occurs during a study visit the study coordinator should first insure the participant receives any needed medical attention. If the study coordinator is notified by phone, the coordinator should confirm that the participant has received medical attention. The study coordinator should then notify the site Principal Investigator and complete the Adverse Event Form within seven days of learning of the event. Study coordinators will comply with local regulations and policies when notifying the institutional IRB.

The following general definitions for rating severity should be used for this study:

**Mild:** Awareness of signs or symptoms, but easily tolerated and transient; causing no loss of time from normal activities; symptoms would not require medication or a medical treatment; signs and symptoms are transient.

**Moderate:** Marked symptoms and discomfort severe enough to cause moderate interference with the subject's usual activities. Symptomatic treatment is possible.

**Severe:** Incapacitating with inability to do work or usual activities; signs and symptoms may be of systemic nature or require medical intervention and/or treatment. Hospitalization may be required or prolonged.

The relationship of an AE or SAE to the underlying disease or to the procedure will be attributed using the following definitions:

Not Related: There is no evidence that the event has a relationship to the drug(s).

**Possibly Related**: The event has a timely relationship to the drug(s) used. However, a potential alternative etiology may be responsible for the adverse event.

**Probably Related**: The event has a timely relationship to the drug(s) used and the causative relationship can clearly be established. No potential alternative etiology is apparent.

The number of subjects and observation time in this pilot study is insufficient to develop a composite index or statistical plan for the evaluation of safety endpoints for this study. Therefore, all adverse events, their timing, severity, and attribution will be reported in study reports.

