## 6.3.2 Serious Adverse Events

The FDA (2009) defines a serious adverse event as an adverse event that: results in the participant's death, is life-threatening, results in hospitalization (initial or prolonged), results in significant, persistent, or permanent change, impairment, damage, disruption, or disability in the participant's body function/structure, physical activities or quality of life, results in a congenital anomaly, or requires intervention to prevent permanent impairment or damage.

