#### 6.3.3 Procedures for Serious Adverse Events

There are no expected serious adverse events (SAE) in this study. In accordance with 21 CFR Parts 803 and 812, an SAE is defined as any untoward medical occurrence that: results in death, is lifethreatening, requires inpatient hospitalization or prolongation of existing hospitalization, results in persistent or significant disability/incapacity, is a congenital anomaly/birth defect, or requires intervention to prevent permanent impairment or damage. All SAE will be reported to [name] and the Data Safety Monitoring Board Chair in 24 hours after knowledge of the occurrence.

If a serious adverse event (SAE) occurs during a study visit the study coordinator should first insure the participant receives any needed medical attention. If the study coordinator is notified by phone, the coordinator should confirm that the participant has received medical attention. The study coordinator should then notify the site Principal Investigator and complete the adverse event form. All SAE will be reported to [name] and the Data Safety Monitoring Board in 24 hours after knowledge of the occurrence. Study coordinators should comply with local regulations and policies when notifying the institutional IRB. The DSMB will review all SAEs and the Chairperson of the DSMB will notify the HRPO and principal investigator of adverse safety outcome information sufficient to stop the study.

The principal investigator has the obligation to report all serious adverse events to the FDA, IRB, and Novartis Pharmaceuticals Drug Safety and Epidemiology Department (DS&E). All events reported to the FDA by the investigator are to be filed utilizing the Form FDA 3500A (MedWatch Form), if applicable

To ensure patient safety, every SAE, regardless of suspected causality, occurring after the patient has provided informed consent and until at least 30 days after the patient has stopped study treatment must be reported to Novartis within 24 hours of learning of its occurrence. Information about all SAEs is collected and recorded on a Serious Adverse Event Report Form. The investigator must assess and record the relationship of each SAE to each specific study treatment (if there is more than one study treatment), complete the SAE Report Form in English, and send the completed, signed form along with the Novartis provided fax cover sheet to the Novartis Oncology Drug Safety and Epidemiology (DS&E) department by fax ([contact]) within 24 hours.

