Any additional information for the SAE including complications, progression of the initial SAE, and recurrent episodes must be reported as follow-up to the original episode within 24 hours of the investigator receiving the follow-up information. An SAE occurring at a different time interval or otherwise considered completely unrelated to a previously reported one should be reported separately as a new event.

Any SAEs experienced after a 30 day safety evaluation follow-up period should only be reported to Novartis if the investigator suspects a causal relationship to the study treatment.

Follow-up information is submitted in the same way as the original SAE Report. Each re-occurrence, complication, or progression of the original event should be reported as a follow-up to that event regardless of when it occurs. The follow-up information should describe whether the event has resolved or continues, if and how it was treated, whether the blind was broken or not, and whether the patient continued or withdrew from study participation.

If the SAE is not previously documented in the Investigator's Brochure or Package Insert (new occurrence) and is thought to be related to the Novartis study treatment, an oncology Novartis Drug Safety and Epidemiology (DS&E) department associate may urgently require further information from the investigator for Health Authority reporting. Novartis may need to issue an Investigator Notification (IN), to inform all investigators involved in any study with the same drug that this SAE has been reported. Suspected Unexpected Serious Adverse Reactions (SUSARs) will be collected and reported to the competent authorities and relevant ethics committees in accordance with Directive 2001/20/EC or as per national regulatory requirements in participating countries.

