## **6.3.4 Pregnancy Procedures and Reporting**

Any participant who becomes pregnant during the study will discontinue study medication and procedures for pregnancy follow-up and reporting will be followed:

To ensure patient safety, each pregnancy occurring while the patient is on study treatment must be reported to Novartis within 24 hours of learning of its occurrence. The pregnancy should be followed up to determine outcome, including spontaneous or voluntary termination, details of the birth, and the presence or absence of any birth defects, congenital abnormalities, or maternal and/or newborn complications.

Pregnancy should be reported by the investigator to the Novartis Oncology Drug Safety and Epidemiology Department (DS&E) by fax ([contact]). Pregnancy follow-up should include an assessment of the possible relationship of the pregnancy outcome to the study treatment. Any SAE experienced during pregnancy must be reported on the SAE Report Form.

Because males will not be enrolled in this study, there is no risk of pregnancy in partners of male participants.

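### Section 6.3.1 ends follow-up of all adverse events, SAEs included, 1 month after study completion; Section 6.3.3 sets no time limit for SAE outcomes, and the two are not reconciled

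*Combined protocol and SAP*

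**What the plan says.** Section 6.3.1 sets the length of follow-up: "All adverse events will be followed until they are adequately resolved or stabilized, or for 1 month following study completion, whichever comes first". The sentence covers every adverse event. Section 6.3.2 makes a serious event a kind of adverse event ("The FDA (2009) defines a serious adverse event as an adverse event that: results in the participant's death, is life-threatening"), so SAEs fall under the same sentence unless something exempts them, and nothing does.

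Section 6.3.3 has its own rules for SAEs:

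- **Onset window.** Every SAE from consent "until at least 30 days after the patient has stopped study treatment must be reported to Novartis within 24 hours of learning of its occurrence".
- **After the window.** "Any SAEs experienced after a 30 day safety evaluation follow-up period should only be reported to Novartis if the investigator suspects a causal relationship".
- **Later course.** "Each re-occurrence, complication, or progression of the original event should be reported as a follow-up to that event regardless of when it occurs".
- **Content of follow-up reports.** "The follow-up information should describe whether the event has resolved or continues, if and how it was treated".

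Section 6.3.4 adds, for pregnancy: "The pregnancy should be followed up to determine outcome, including spontaneous or voluntary termination, details of the birth".

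The documents do not define study completion. Section 4.4 puts the end of the study at 56 days, and Section 5.4 labels the 2-month visit as the end of study.

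**The concern.** The earlier-of rule in 6.3.1 affects only events that have neither resolved nor stabilised by the cap. Those are the events whose final outcome is most informative. A coordinator who follows 6.3.1 may close such an SAE at 1 month, while 6.3.3 still expects a report on whether it resolved and on any later progression. The site would be asked for information that it had been told it could stop collecting.

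Safety of imatinib in LAM is one of the specific aims, and Section 6.3 sets the goal of capturing every adverse event. Section 6.3.1 also says the trial is too small for a statistical safety plan and that events will be reported individually. The individual event records are therefore the safety result, and duration is one of the items to be recorded. An SAE closed while still ongoing has neither a duration nor an outcome.

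This point is about following events already known to the site. It is not about how events are detected.

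**Working it through.** The plan gives no figure to reproduce, so the check compares the two rules and then works out the timing.

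**Side by side**

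| | Section 6.3.1 | Section 6.3.3 |
|---|---|---|
| Events covered | all adverse events | SAEs |
| Nature of the duty | follow the event | report the event and its later course |
| End point | earlier of resolution/stabilisation and completion + 1 month | none stated |
| Onset window | none stated | consent to at least 30 days after last dose; later if suspected related |

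The conflict is between a capped duty and an uncapped one. It is not between two stated durations.

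**Timing inputs**

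- C, day of study completion: 56 (Section 4.4), read as the participant's own last visit (assumption).
- L, day of last dose: not stated; taken as 56 (assumption).
- M, length of 1 month: 28 to 31 days.
- Minimum SAE window: 30 days after last dose (Section 6.3.3).

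**Formulas**

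- Cap = C + M.
- End of minimum window: W = L + 30.
- Follow-up left for an SAE starting on day d = (C + M) − d.
- Follow-up left for an SAE starting on day W = (C − L) + (M − 30).

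**Results with C = L = 56**

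- Cap: 56 + 28 = Day 84 to 56 + 31 = Day 87.
- W: 56 + 30 = Day 86.
- Onset on Day 86: 84 − 86 = −2 to 87 − 86 = +1 days left.
- Onset on Day 79: 84 − 79 = 5 to 87 − 79 = 8 days left.
- Onset on Day 56: 84 − 56 = 28 to 87 − 56 = 31 days left. Any earlier onset has more.
- A related SAE starting after Day 87 is already past the cap for every month length.

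**Sensitivity**

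- Calendar months, with completion and last dose at about Day 61: cap is Day 89 to 92 and W is Day 91. The margin at W is again −2 to +1 days, because it depends only on C − L and M.
- Drug stopped on Day 28 but participant stays to Day 56: W = 28 + 30 = Day 58, and the margin is (56 − 28) + (M − 30) = 26 to 29 days. The near-coincidence disappears.

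**The case against.** The strongest objection is that the contradiction and the harm pull against each other. If 6.3.3 is a real duty to follow SAEs, they have no cap and nothing is lost. If 6.3.3 only requires information to be passed on once the site has it (new information is due within a day of receipt), it can coexist with a limit on active follow-up. SAEs also have their own section, and the usual reading is that the specific rule overrides the general one. This stands in part. It removes certainty about the harm, but not the need to say which rule applies. On the second reading an unresolved SAE is reported only if news of it happens to reach the site.

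A reader might infer several stronger things that the documents do not support:

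- **That outcomes of late SAEs are unknown by rule.** This follows only if 6.3.1 governs SAEs.
- **That late SAEs typically get about two weeks of follow-up.** With a Day 86 cap and equally likely onset over Days 57 to 86, the mean is (29 + 0)/2 = 14.5 days. That counts only onsets after treatment. Over Days 1 to 86 the mean is (85 + 0)/2 = 42.5 days. The documents give no onset distribution, so neither figure measures the defect.
- **That study completion may mean the end of the whole trial.** Section 8.2.1 uses the term that way for leftover biosamples. Sections 4.4, 5.2 and 5.4 favour the participant's own last visit. A definition is still needed for people who withdraw, or who leave after a 10% fall in FEV1 or FVC (Sections 6.4 and 6.4.1), because they never reach that visit.
- **That every non-serious, possibly related event needs open-ended follow-up.** Nothing in 6.3.3 requires this. A 1-month limit for such events in a 2-month pilot is a legitimate design choice.

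**Conclusion.** The point holds as an unreconciled pair of rules. Section 6.3.1 caps follow-up of all adverse events without exempting SAEs, and 6.3.3 expects the later course and outcome of SAEs without a limit. Pregnancy is a further case: 6.3.4 follows it to outcome, and a birth defect is an SAE under 6.3.3, so both can fall well beyond the cap.

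If 6.3.1 is applied literally, the effect is concentrated in SAEs that start near the end of the minimum window. These get between none and about a week of active follow-up, against about 4 weeks or more for SAEs starting on treatment. This rests on the last dose being taken at the Day 56 visit, on completion meaning the participant's own last visit, and on 30 days being only the minimum window. It does not apply to someone who stops drug early but stays in the study.

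No endpoint, analysis or sample size is affected. The change is worth making because it is cheap and protects a safety record that is a stated aim.

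**What to change.** Reconcile Sections 6.3.1, 6.3.3 and 6.3.4:

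1. Limit the earlier-of cap in 6.3.1 to non-serious events.
2. State that SAEs are followed, by telephone if needed, until resolved or stabilised, with final outcome and its date recorded. Cross-refer to 6.3.3, and to 6.3.4 for pregnancy.
3. Define study completion as the participant's own last visit or, for those who withdraw, the date of leaving the study. Follow-up after withdrawal remains subject to the participant's choices under Section 6.4.1.

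The definition alone would not be enough. For someone whose last dose and departure fall on the same day, C − L = 0 and the margin at the end of the window is still −2 to +1 days, so the SAE exemption is the part that matters.

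The cost is a short wording change, a few extra calls in a 20-person trial, and the possibility that the database has to be updated late when an outcome arrives after closure.
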